## **8.2 Secondary Objectives**

1. SO1: To compare proportions of preterm birth after RIV4 versus IIV4 vaccination.

This proportion will be compared between the RIV4 group and the IIV4 group using an exact Mantel-Haenszel statistic (calculated in Proc Logistic in SAS) in a stratified analysis by site to control for the randomization blocks at the two-sided alpha 0.05 level. The site adjusted odds ratio and corresponding 95% confidence interval for the proportion of preterm birth will also be calculated.

2. SO2: To compare proportions of combined fetal death and neonatal death after RIV4 versus IIV4 vaccination.

These proportions will be compared between the RIV4 group and the IIV4 group using an exact Mantel-Haenszel statistic (calculated in Proc Logistic in SAS) in a stratified analysis by site to control for the randomization blocks at the two-sided alpha 0.05 level. The site adjusted odds ratio and corresponding 95% confidence interval for the proportions of combined fetal death and neonatal death will also be calculated.

3. SO3: To compare proportions of spontaneous abortion after RIV4 versus IIV4 vaccination.

This proportion will be compared between the RIV4 group and the IIV4 group using an exact Mantel-Haenszel statistic (calculated in Proc Logistic in SAS) in a stratified analysis by site to control for the randomization blocks at the two-sided alpha 0.05 level. The site adjusted odds ratio and corresponding 95% confidence interval for the proportion of spontaneous abortion after vaccination will also be calculated. This will be a subgroup analysis of only those participants vaccinated at less than 20 weeks gestational age.

4. SO4: To compare proportions of moderate/severe solicited reactogenicity events in pregnant women vaccinated with RIV4 versus IIV4 (tables 2 and 3 below).

Reactogenicity will be assessed for 8 days following the vaccination at Visit 1. These proportions will be presented by treatment group, symptom, and grade level (moderate/severe) for women with injection site reactogenicity within 8 days post-vaccination. These proportions will be compared between the RIV4 group and the IIV4 group, within symptom, using an exact Mantel-Haenszel statistic (calculated in Proc Logistic in SAS) in a stratified analysis by site to control for the randomization blocks at the two-sided alpha 0.05 level. Systemic reactogenicity will be presented in a similar fashion. There will be 14 comparisons performed.

**Table 2: Injection-site Reactogenicity\***

Symptom	Mild (Grade 1)	Moderate (Grade 2)	Severe (Grade 3)
Pain	Noticeable but does not interfere with activity	Interferes with activity but did not necessitate medical visit or absenteeism	Prevents daily activity and resulted in medical visit or absenteeism
Tenderness	Noticeable but does not interfere with activity	Interferes with activity but did not necessitate medical visit or absenteeism	Prevents daily activity and resulted in medical visit or absenteeism
Induration/ Swelling	25 to ≤50 mm	51 to ≤100 mm	>100 mm
Erythema	25 to ≤50 mm	51 to ≤100 mm	>100 mm

\*Injection-site criteria being used in the CISA Study on Safety of RIV4 versus IIV4 in Pregnant Women

**Table 3: System Reactogenicity\***

Systemic	Mild (Grade 1)	Moderate (Grade 2)	Severe (Grade 3)
Fever **	≥100.4 to ≤101.1° F	≥101.2 to ≤102.0° F	≥102.1° F
Malaise (Fatigue)	Noticeable but does not interfere with activity	Interferes with activity but did not necessitate medical visit or absenteeism	Prevents daily activity and resulted in medical visit or absenteeism
Myalgia (Body aches)	Noticeable but does not interfere with activity	Interferes with activity but did not necessitate medical visit or absenteeism	Prevents daily activity and resulted in medical visit or absenteeism
Arthralgia (Joint pain)	Noticeable but does not interfere with activity	Interferes with activity but did not necessitate medical visit or absenteeism	Prevents daily activity and resulted in medical visit or absenteeism
Nausea	Noticeable but does not interfere with activity	Interferes with activity but did not necessitate medical visit or absenteeism	Prevents daily activity and resulted in medical visit or absenteeism
Vomiting	Noticeable but does not interfere with activity	Interferes with activity but did not necessitate medical visit or absenteeism	Prevents daily activity and resulted in medical visit or absenteeism
Diarrhea	Noticeable but does not interfere with activity	Interferes with activity but did not necessitate medical visit or absenteeism	Prevents daily activity and resulted in medical visit or absenteeism
Abdominal pain	Noticeable but does not interfere with activity	Interferes with activity but did not necessitate medical visit or absenteeism	Prevents daily activity and resulted in medical visit or absenteeism

Headache	Noticeable but does not interfere with activity	Interferes with activity but did not necessitate medical visit or absenteeism	Prevents daily activity and resulted in medical visit or absenteeism
Chills/shivering	Noticeable but does not interfere with activity	Interferes with activity but did not necessitate medical visit or absenteeism	Prevents daily activity and resulted in medical visit or absenteeism

\*\* Oral temperature, no recent hot/cold beverages or smoking

### 8.3 Exploratory Objectives

1. EO1: To compare and describe serious adverse events (SAE) in pregnant women vaccinated with RIV4 and IIV4.

The proportion and 95% exact binomial confidence interval of the number of participants with serious adverse events (SAEs), as well as the total number of events, will be presented by site, vaccine group, severity, and relatedness. Listings of these SAEs will also be presented. Non-overlapping confidence boundaries will be an indication of a statistical difference between the groups. These presentations and listings will be provided for the participant's study duration and for the first 42 days after vaccination. Note the study monitoring period for each participant is up to 90 days post-partum.

2. EO2: To compare proportions of adverse birth outcomes of clinical interest after RIV4 versus IIV4 vaccination.

These proportions (i.e., infants born small-for-gestational age, pregnant women with clinical chorioamnionitis, and pregnant women with preeclampsia or eclampsia) will be compared between the RIV4 group and the IIV4 group using an exact Mantel-Haenszel statistic (calculated in Proc Logistic in SAS) in a stratified analysis by site to control for the randomization blocks at the two-sided alpha 0.05 level.

3. EO3: To compare proportions of severe local and/or solicited reactogenicity events in pregnant women vaccinated with RIV4 versus IIV4 and describe proportions of solicited reactogenicity events by severity grade in pregnant women vaccinated with RIV4 versus IIV4

The proportion of pregnant women with one or more severe local and/or solicited reactogenicity event within 8 days after vaccination with RIV4 versus IIV4. The proportion of participants with  $\geq 1$  local, severe, and local or severe reaction will be compared between the RIV4 group and the IIV4 group using an exact Mantel-Haenszel statistic (calculated in Proc Logistic in SAS) in a stratified analysis by site to control for the randomization blocks at the two-sided alpha 0.05 level for the three comparisons.

We will also describe the proportions of pregnant women with each reactogenicity events by severity grade after RIV4 and IIV4 vaccination. The severity grades are: any, mild, moderate and severe as noted above in Tables 2 and 3.

4. EO4: To compare and describe health outcomes through 90 days of life in infants born to women after RIV4 versus IIV4 vaccination.

The proportion of infants with medically-attended events through 90 days of life and the proportion of infants with neonatal death will be compared between the RIV4 group and the IIV4 group using an exact Mantel-Haenszel statistic (calculated in Proc Logistic in SAS) in a stratified analysis by site to control for the randomization blocks at the two-sided alpha 0.05 level. The proportion and 95% exact binomial confidence interval of SAEs in infants through 90 days of life, as well as the total number of events, will be presented by site, vaccine group, severity, and relatedness. Listings of these SAEs will also be presented. Non-overlapping confidence boundaries will be an indication of a statistical difference between the groups.

5. EO5: To compare maternal immune responses to influenza antigens and calculate the post and pre-vaccination ratio after RIV4 versus IIV4 vaccination.

The proportion of pregnant women achieving seroconversion at day 29 and the proportion pregnant women with a seroprotective HAI titer ( $\geq 1:40$ ) pre- and post-immunization at day 29 will be compared using a Mantel-Haenszel statistic in a stratified analysis by site to control for the randomization blocks at the two-sided alpha 0.05 level. The geometric mean HAI titer (GMT) pre- and post-immunization at day 29 after RIV4 versus IIV4 vaccination for each influenza vaccine antigen will be compared (within vaccine arm pre versus post and within timeframe RIV4 versus IIV4) using a regression model with the log transformed titer value at the two-sided alpha 0.05 level. The proportion and 95% exact binomial confidence interval will also be presented in tabular format for each group. The Immunogenicity Population is the primary analysis population. The Maternal Immunogenicity Population is the primary analysis population.

6. EO6: To compare cord blood antibody levels for influenza antigens after RIV4 versus IIV4 vaccination.

The proportion of infants with cord blood seroprotective HAI titer will be compared using a Mantel-Haenszel statistic in a stratified analysis by site to control for the randomization blocks at the two-sided alpha 0.05 level. Infant cord blood geometric mean HAI titer (GMT) for each influenza vaccine antigen will be compared using a regression model with the log transformed titer value at the two-sided alpha 0.05 level.

The ratio and 95% confidence interval for cord blood to maternal influenza antibody titers at time of delivery for each influenza vaccine antigen after maternal RIV4 versus IIV4 vaccination will be presented. Non-overlapping confidence boundaries will be an indication of a statistical difference between the groups. The proportion and 95% exact binomial confidence interval will also be presented in tabular format for each group. The Immunogenicity Population is the primary analysis population.

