#### **4.3 Sample Size and Power**

Allowing for a 5% drop out rate and given an initial N=430, there should be approximately 408 pregnant women participants for evaluation. We assume that 15% of pregnant women will have adverse birth outcomes after vaccination with RIV4 or IIV4, based on national and CISA site estimates of preterm birth rates. We have selected a clinically meaningful noninferiority margin of 10%. Statistical calculations show that with a one-sided alpha of 0.025 and 204 subjects in each group across all study sites, there is approximately 81% power to reject the null hypothesis that RIV4 is inferior to IIV4 in the proportion of adverse birth outcomes.

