#### **5.2 Analytic Issues**

There are three study sites participating in the study and analysis of the primary objective will be stratified by site (Duke, Boston, Cincinnati) to account for this unit of randomization. All objectives will be stratified by site when applicable. There is one primary objective being evaluated, using a noninferiority hypothesis at the one-sided alpha 0.025 level. Otherwise, the alpha level will be set at two-sided alpha 0.05 for the secondary objectives and all exploratory objectives.

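### Maternal SAEs, infant SAEs and the cord-to-maternal titre ratio are compared only by whether two separate 95% intervals fail to overlap, a rule far stricter than the plan's two-sided 0.05

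*SAP*

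**What the plan says.** SAP 5.2 fixes the significance level: "Otherwise, the alpha level will be set at two-sided alpha 0.05 for the secondary objectives and all exploratory objectives". On site it adds: "All objectives will be stratified by site when applicable".

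SAP 8.3 then treats three outcomes differently from the rest:

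- **Maternal SAEs (EO1; protocol 7.3.8).** The proportion of women with an SAE is shown with an exact binomial 95% interval, tabulated by site, vaccine group, severity and relatedness. This is done for the first 42 days and for the whole study.
- **Infant SAEs (EO4; protocol 7.3.10).** The summary is "The proportion and 95% exact binomial confidence interval of SAEs in infants through 90 days of life", tabulated in the same way.
- **Cord-to-maternal ratio (EO6; protocol 7.3.12).** The summary is "The ratio and 95% confidence interval for cord blood to maternal influenza antibody titers at time of delivery", for each antigen and arm.

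All three carry the same criterion: "Non-overlapping confidence boundaries will be an indication of a statistical difference between the groups". No test, risk difference, odds ratio or ratio of ratios is defined for them.

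Other outcomes in the same objectives do have a direct comparison. In EO4, "The proportion of infants with medically-attended events through 90 days of life and the proportion of infants with neonatal death will be compared between" the arms by a site-stratified exact Mantel-Haenszel test at two-sided 0.05. In EO6, cord seroprotection has a Mantel-Haenszel test and cord GMT a regression on log titre, both at two-sided 0.05.

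**The concern.** Checking whether two separate 95% intervals overlap is not a 5% test of the difference. Non-overlap requires the estimates to differ by more than the sum of the two half-widths, whereas a test of the difference compares it with the square root of the sum of squares, which is smaller. The rule therefore errs towards not flagging a real difference.

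That direction matters for SAEs. The trial's rationale is the lack of systematically collected safety data on RIV in pregnancy (protocol 1.2). No data safety monitoring board is planned, and the interim review reads SAE narratives from the first season only (protocol 7.3.14). The final SAE table is thus the planned overall comparison of SAEs between arms. An imbalance that is significant at the plan's own level could receive no statistical indication of a difference. For the titre ratio, a difference in placental antibody transfer could go unflagged; that is an immunogenicity matter, not a safety one.

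**Working it through.** **Inputs.** From SAP 4.3: 204 evaluable women per arm (430 × 0.95 = 408.5, about 408). From SAP 5.2: two-sided 0.05. From SAP 8.3: exact binomial (Clopper-Pearson) 95% intervals for SAEs. The documents give no SAE rate, so a range is assumed.

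**The plan's own figure.** The only stated power is for the primary test, about 81%. With 15% in each arm and a 10-point margin, SE = √(2 × 0.15 × 0.85 / 204) = 0.03536. Power = Φ(0.10/0.03536 − 1.96) = Φ(0.868) = 80.7%, which agrees. No power is stated for the three outcomes here.

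**Size of the rule, normal case.** With independent arms and a common standard error s, intervals fail to overlap when the difference exceeds 2 × 1.96 × s. The standard error of the difference is √2 × s, so the critical value is √2 × 1.96 = 2.772.

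- Two-sided size = 2 × (1 − Φ(2.772)) = 0.0056, about one ninth of 0.05.
- With standard errors in the ratio 2:1 it is 0.0085, and at 3:1 it is 0.013.
- Intervals of about 83.4%, not 95%, would give 0.05.

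**SAEs, no true difference.** Probabilities summed over all outcomes of two binomials, n = 204 each:

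| Rate in both arms | Non-overlap | Fisher p ≤ 0.05 |
|---|---|---|
| 2% | 0.12% | 1.8% |
| 5% | 0.25% | 2.9% |
| 10% | 0.34% | 3.4% |
| 20% | 0.38% | 3.7% |

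Fisher's test is itself below nominal, so the gap does not come from choosing a liberal comparator.

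**SAEs, true difference.** The site-stratified exact test was simulated with 40,000 trials and three equal sites of 68 per arm (an assumption):

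| True rates | Non-overlap | Fisher | Site-stratified exact |
|---|---|---|---|
| 2% v 4% | 3% | 14% | 14% |
| 5% v 12% | 35% | 67% | 67% |
| 10% v 20% | 48% | 78% | 78% |
| 10% v 25% | 88% | 98% | 98% |

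At 2% v 4% neither approach is informative.

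**In counts.** With 10/204 in one arm:

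- Fisher's p first falls to 0.05 or below at 22/204 in the other arm (p = 0.041).
- The intervals first separate at 27/204 (p = 0.005).
- At 26/204 the intervals are 2.4% to 8.8% and 8.5% to 18.1%. They overlap, yet p = 0.008.

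**Titre ratio.** On the log scale with equal standard errors, an effect with 80% power at two-sided 0.05 lies 1.960 + 0.842 = 2.802 standard errors of the difference from zero. Under non-overlap its power is Φ(2.802 − 2.772) = 51%. An effect with 90% power falls to Φ(3.242 − 2.772) = 68%. Restoring 80% would take ((2.772 + 0.842)/2.802)² = 1.66 times the sample.

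**The case against.** The best case for leaving the text alone has four parts.

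1. **The outcomes are exploratory and the wording is soft.** The plan calls non-overlap an indication, does not say that overlap means no difference, and attaches no decision to it. This is true and limits the seriousness. But SAP 5.2 applies 0.05 to exploratory objectives explicitly, and the plan offers nothing to read when intervals overlap.
2. **The band of disagreement is narrow and visible.** Against 10/204, the rule and Fisher's test differ only for 22 to 26 events, and all counts and intervals are still reported. A reader could compute a contrast. That leaves it to be chosen after the results are known, when it can be specified now.
3. **Much of the safety content is tested elsewhere.** Preterm birth, fetal and neonatal death, spontaneous abortion, preeclampsia or eclampsia, chorioamnionitis and infant medically-attended events have their own tests. Cord GMT and seroprotection are tested too. This stands as mitigation. The overall SAE proportions and the ratio itself still have no direct comparison.
4. **The figures are conditional.** SAE rates are assumed, and the safety population is mITT, so up to 215 per arm. With 215, non-overlap has 38% power against Fisher's 70% at 5% v 12%, and 51% against 80% at 10% v 20%. The gap hardly moves. For the ratio, unequal standard errors soften the rule somewhat, but at 3:1 its size is still 0.013.

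The point about site is weaker on its own, because SAP 5.2 asks for stratification only when applicable and SAEs are tabulated by site. What is missing is a pooled, site-adjusted contrast.

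**Conclusion.** The concern holds and should be fixed before analysis. The between-arm rule for these three outcomes does not operate at the level SAP 5.2 sets. Its size is about 0.0056 in the equal-standard-error case and 0.0012 to 0.0038 for SAEs with exact intervals. For SAE differences from 5% v 12% to 10% v 25%, it gives up about 10 to 32 points of power against an exact test.

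This rests on assumed SAE rates, 204 per arm, three equal sites for the stratified figures, and independent arms with equal standard errors for the ratio figures. Confidence in the conclusion is high, since no plausible change to these assumptions brings the rule near 0.05. The primary endpoint, its components and the secondary outcomes are not affected.

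**What to change.** Delete the non-overlap sentence from SAP 8.3 (EO1, EO4, EO6) and from protocol 7.3.8, 7.3.10 and 7.3.12, and specify instead:

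- **SAEs.** Compare the proportions of women, and of infants, with at least one SAE by the site-stratified exact Mantel-Haenszel test already used in SAP 8.3. Report the risk difference with the site-stratified Newcombe 95% interval already used in SAP 8.1. Apply this to both maternal windows (42 days and whole study). State that the infant measure is infants with at least one SAE, because the present wording can be read as a proportion of events.
- **Cord-to-maternal ratio.** For each antigen, regress the log ratio on arm and site, and report the ratio of geometric mean ratios with its 95% interval. State how titres below the 1:10 starting dilution are handled.
- **Description.** Keep the per-arm intervals, the tables by site, severity and relatedness, and the listings, as description only.

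The cost is wording in two documents and modest additions to existing programs. A few more nominally significant exploratory results may appear; protocol 7.3.2 already says these are not adjusted for multiplicity. The primary test, secondary tests and sample size do not change.

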	7.1 Definitions	
	7.2 Sample Size and Power Estimation	
	7.3 Analysis Plan	
	7.3.1 Study Populations	
	7.3.2 Alpha Level	
	7.3.3 Primary Objective	
	7.3.4 Secondary Objective 1	
	7.3.5 Secondary Objective 2	
	7.3.6 Secondary Objective 3	
	7.3.8 Exploratory Objective 1	
	7.3.9 Exploratory Objective 2	
	7.3.10 Exploratory Objective 3	

	7.3.11	Exploratory Objective 4	27
	7.3.12	Exploratory Objective 4 Exploratory Objective 5	27
	7.3.13	Sensitivity analysis	27
	7.3.14	Interim Safety Data Review	28
	7.3.16	Further analysis	28
	7.4 DATA	Management Plan	28
	7.4.1 Re	search Electronic Data Capture (REDCap)	29
	7.4.2	Role of the CDC Investigators in the Project	30
8	HUMAN	N PARTICIPANTS	30
	8.1 Hum	AN PARTICIPANTS INVOLVEMENT, CHARACTERISTICS, AND DESIGN	30
	8.2 Sour	CES OF MATERIAL	30
	8.3 POTE	NTIAL RISKS AND BENEFITS	30
	8.4 ADEQ	UACY OF PROTECTION AGAINST RISKS	31
	8.4.1	Protections against Risk	31
	8.4.2	ClinicalTrials.gov Requirements	32
	9.0 Hum	AN PARTICIPANTS	32
	9.1.1	Vulnerable Subjects Research	32
RI	EFERENCES	S	33

PROTOCOL SUMMARY

Title:	A Prospective, Randomized, Clinical Trial to Compare Adverse Birth Outcomes in Pregnant Women Receiving Quadrivalent Recombinant Influenza Vaccine (RIV4) versus Quadrivalent Inactivated Influenza Vaccine (IIV4)	
Phase:	Phase 4	
Population:	430 adult pregnant women ≥ 18 years at ≤ 34 weeks gestation who plan on receiving RIV4 or IIV4 during the current pregnancy in accordance with the Advisory Committee on Immunization Practices (ACIP) and American College of Obstetricians & Gynecologists (ACOG) national recommendations.	
Clinical Sites:	Three: Duke University (Lead); Cincinnati Children's Hospital Medical Center (Contributor); Boston Medical Center (Contributor)	
Study Duration: 60 months (approximately 12 months to recrumaximum of 24 months to follow, 24 months to perform and laboratory assays		
Participant Duration:	Up to 12 months depending upon gestational age at enrollment and delivery. Will be followed for 90 days postpartum.	
Description of Study Procedures:	This is a prospective, randomized clinical trial. During the study, pregnant women will be randomized (1:1) to receive RIV4 or IIV4. Vaccines will be administered by licensed providers.	
	Prior influenza vaccine history will be verified by medical record review when possible.	

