4.3 Recruitment

Pregnant women at \leq 34 weeks, \geq 18 years old, who are planning to receive influenza vaccination during their current pregnancy will be recruited at prenatal clinics whose patients deliver at Duke University Hospital (Duke), University of Cincinnati Medical Center (Cincinnati), or Boston Medical Center (Boston). Pregnant women will be prescreened for eligibility via medical record review. The study will be introduced to a potential participant by a member of their care team. Potential participants that fall within the \leq 34 weeks gestation range will be approached by a member of the research team for study enrollment. Medical and obstetric history, including prior influenza vaccine history, will be obtained via participant self-report with verification by chart review whenever feasible (including medical records, employee health records, immunization registry records, and pharmacy records).

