5 STUDY SCHEDULE, PROCEDURES, & EVALUATIONS

5.1 Schedule of events

Pregnant women meeting the proposed eligibility criteria will be recruited. Written informed consent (will be obtained from study participants prior to conducting any study procedures. **Table 1** describes the proposed schedule of study visits with further details below.

Table 1. Study Visit Schedule									
Procedure	Screening Visit* Day -30 to 1	Visit 1 Day 1	Visit 2 Day 4 + 1	Visit 3 Day 9 + 3	Visit 4 Day 29 -7/+14	Visit 5 Day 43 + 7	Visit 6 Delivery	Visit 7 Postnatal Day 90 + 14	Unscheduled Visit
Type of contact	Chart Abstraction/ Clinic	Clinic	Phone/Text/ Email/Data Review	Phone/Text /Email/Data Review	Clinic	Phone/Text/ Email/Chart Abstraction	Hospital/ Chart Abstraction	Phone/Text/ Email/Chart Abstraction	Clinic
Informed consent & Medical Release of Information	Х								
Review Eligibility Criteria	Х	Х							
Demographic, Medical, and obstetric history	Х	Х							
Influenza Vaccination History	X	Х							
Vital signs (temperature, blood pressure, and heart rate)		Х							Х
Blood Sample Collection		Х			Х		X ¹		
Randomization and Vaccination		Х							
Obtain immediate adverse event information		Х							
Dispense memory aid		Х							
Dispense study supplies		Х							
Complete Memory aid form (REDCap or paper)		Х	Х	Х					
Concomitant medications/vaccinations	Х	Х	Х	Х	Х	Х	Х	Х	Х
Obtain solicited adverse events		Х	Х	Х					
Obtain unsolicited adverse events		Х	Х	Х					Х
Obtain serious adverse event information		Х	Х	Х	Х	Х	Х	Х	Х
Infant data collection								Х	

¹Cord blood and maternal blood collection at Visit 6 will be optional and collected when feasible by the site.

Screening Visit, Study Day -30 to 1 (Chart Abstraction & Clinic Visit – may occur simultaneously with Visit 1)

- Obtain written informed consent and release of medical record information
- Review and confirm study eligibility
- Obtain information on preferred method of contact for follow-up (telephone or email reminder or text reminder)
- Obtain demographic data
- Obtain influenza vaccination history
- Obtain medical history (e.g. chronic hypertension, diabetes, autoimmune disorder), obstetric history (e.g. parity, prior preterm birth, low birthweight, small for gestational age), and current pregnancy status (e.g. gestational diabetes, gestational hypertension, placenta previa, estimated due date)
- Obtain concomitant medication use

Visit 1, Study Day 1 - Screening, Enrollment, and Vaccination (Clinic Visit)

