## 7 BASELINE DATA AND FLOW CHART

### 7.1 Presentation of Baseline Data

The following baseline information will be presented by treatment group, age, ethnicity, race and tobacco, marijuana or other substance use, gestational age at vaccination, study enrollment site, and influenza season of enrollment. Summary statistics (e.g., mean, standard deviation, median) will be presented for continuous variables. Categorical variables will be described with frequencies and percentages. Specific medical issues (i.e., hypertension, diabetes, and prior preterm birth) will also be presented.

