## **10 FURTHER ANALYSIS**

If the error in stratification by gestational age results in an imbalance in gestational age between the treatment groups, evaluation of secondary outcomes by treatment group will be done using gestational age as a covariate if specified analyses can adjust for this factor. To have reasonable results, each cell count needs to be 5 or greater.

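### Influenza vaccination history is collected before randomisation but appears in no baseline table and no antibody analysis; the cost is modest precision and an undisplayed chance imbalance, not validity

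*SAP*

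**What the plan says.** **Collection.** Protocol 4.3 says that medical and obstetric history, "including prior influenza vaccine history, will be obtained via participant self-report with verification by chart review whenever feasible". The Protocol Summary is equally conditional: "Prior influenza vaccine history will be verified by medical record review when possible". In the Protocol 5.1 visit schedule the item has its own row, marked at Screening and Visit 1 ("Obtain influenza vaccination history").

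**Baseline table.** The SAP 7.1 list runs from age to "gestational age at vaccination, study enrollment site, and influenza season of enrollment", and adds: "Specific medical issues (i.e., hypertension, diabetes, and prior preterm birth) will also be presented". Prior influenza vaccination is not there.

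**Analysis.** SAP 8.3 numbers the maternal antibody objective EO5 and the cord-blood objective EO6 (they are EO4 and EO5 in the protocol and in SAP 2.3). Under both, the proportions "will be compared using a Mantel-Haenszel statistic in a stratified analysis by site". Geometric mean titres are compared "using a regression model with the log transformed titer value at the two-sided alpha 0.05 level", and no covariate is named.

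**Elsewhere.** SAP 9 covers wrong treatment and protocol violations. SAP 10 is the only place where a covariate is foreseen: "evaluation of secondary outcomes by treatment group will be done using gestational age as a covariate if specified analyses can adjust for this factor". That covers gestational age, the secondary outcomes only, and only if there is an imbalance. SAP Appendix 1 uses influenza vaccine receipt to exclude women vaccinated earlier in the current season.

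**The concern.** A variable fixed before randomisation, and plausibly related to antibody level, is gathered with some effort and then left out of the antibody results. If it predicts response, two things are lost. Variation between previously vaccinated and unvaccinated women stays in the error term. And the reader cannot see whether the arms happened to differ in it. The protocol gives immunogenicity as part of the trial's rationale (Protocol 1.1 and 1.2), so readers of the HAI results are likely to ask. If the adjustment is not specified before analysis, adding it later becomes a post hoc choice.

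**Working it through.** **1. The plan's own figures.** SAP 4.3 gives about 81% power for the primary endpoint: 15% in both arms, margin 10 points, one-sided 0.025, 204 per arm. SE = √(2 × 0.15 × 0.85 / 204) = 0.03536, and power = Φ(0.10/0.03536 − 1.96) = Φ(0.868) = 80.7%. Enrolment: 408/0.95 = 429.5, so 430. Both reproduce, and neither depends on this point. The documents give no power or sample size for the antibody endpoints.

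**2. Assumptions.** The documents state neither how many women were previously vaccinated nor how that affects response. Steps 3 and 4 assume 50-70% previously vaccinated (q), seroconversion of 30-40% in them (a) and 60% in the others (b), 190 evaluable women per arm, and a true contrast of 50% v 64%.

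**3. Variance explained by history.** R² = q(1−q)(a−b)² / [p(1−p)], with p = qa + (1−q)b.

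| q | a | p | R² |
|---|---|---|---|
| 0.7 | 0.40 | 0.46 | 0.21 × 0.04 / 0.2484 = 0.034 |
| 0.5 | 0.40 | 0.50 | 0.25 × 0.04 / 0.25 = 0.040 |
| 0.7 | 0.30 | 0.39 | 0.21 × 0.09 / 0.2379 = 0.079 |
| 0.5 | 0.30 | 0.45 | 0.25 × 0.09 / 0.2475 = 0.091 |

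**4. What that is worth at best.** SE = √[(0.25 + 0.2304)/190] = 0.0503, so the standardised difference is 0.14/0.0503 = 2.784.
- Unadjusted: Φ(2.784 − 1.96) = 79.5%.
- R² = 0.034: Φ(2.784/√0.966 − 1.96) = 80.9%.
- R² = 0.091: Φ(2.784/√0.909 − 1.96) = 83.2%.

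The gain is 1.4 to 3.7 points, if adjustment itself costs nothing.

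**5. Cost of adjustment in a regression.** Yes/no/unknown adds two parameters. With 380 women and no effect of history, the variance rises by about 2/374 = 0.5%, which lowers power by about 0.2 points. Simulation of the log-titre regression at 380 women agrees: under 0.5 points lost with no effect, about 1 to 4 gained with a moderate one.

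**6. Cost of adjustment by stratifying the Mantel-Haenszel test.** Here the information lost in sparse strata matters. Simulated power for 50% v 64% at 190 per arm, with equal sites, 60% previously vaccinated and 10% unknown:

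| Effect of history | Site only (3 strata) | Site × yes/no/unknown (9 strata) |
|---|---|---|
| None | 79.7% | 78.4% |
| 20 points | 78.7% | 79.1% |
| 30 points | 78.3% | 80.9% |

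With six strata (site × yes/no), 204 per arm and a 12-point difference from 45%, power moved from about 69% to between 68% and 72%. Type I error was 4.8-5.5% with or without the extra stratum. In a cord-blood sample of 60-80 women, 80% from one site, nine strata ranged from a loss of 3 to 4 points to a gain of about 1.

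**7. Chance imbalance.** The 95% range of the difference between arms in prior vaccination is ±1.96√[2q(1−q)/204]: ±9.7 points at q = 0.5, and ±8.9 at q = 0.3 or 0.7. Multiplied by a 10 to 30 point effect of history, this shifts the unadjusted difference by ±0.9 to ±2.9 points. The shift averages zero over randomisations.

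**8. Eligibility.** Protocol exclusion 1 names receipt in either season before enrolment. Read literally, a woman enrolling in 2020-21 who was vaccinated in 2019-20 is excluded, so prior-season vaccination would be constant that season. SAP Appendix 1 item 1e refers to the vaccine of the year in question, which is narrower.

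**The case against.** The strongest reply is that the premise is imported. The documents never say that prior-season vaccination predicts HAI response. The nearest text, in SAP Appendix 1, concerns receipt in the same season. This stands: every figure above except those in step 1 is illustrative.

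Second, pre-existing immunity is partly covered. EO5 compares pre-vaccination titres and seroprotection between arms, seroconversion is defined relative to baseline titre, and the post/pre ratio is an endpoint. This also stands in part. An imbalance in baseline antibody would be seen, but vaccination history itself would not, and baseline titre is not a named covariate either.

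Third, site-by-history strata are not free. Step 6 bears this out, above all for cord blood, which is collected outside the lead site only if feasible. SAP 4.4 and 10 themselves ask for cell counts of 5 or more before adjusting for gestational age.

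A reader might go further and infer that the comparisons are biased, that the history is fully verified against records, or that the SAP ignores vaccine receipt altogether. The documents do not support these. Treatment is randomised, verification is conditional, and current-season receipt governs eligibility and the population exclusions. Nor can it be said that the needed field is already on the case report form, which is not among the documents.

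**Conclusion.** The omission is real and minor. The endpoints are exploratory, with no alpha adjustment and no power target, and the primary analysis is untouched. Type I error stays near 5% either way. What is lost is roughly 0 to 4 power points, if prior vaccination explains 3-9% of the variance in response, and the display of a chance imbalance that could reach about 9 to 10 points. The size of the gain rests on prevalences and effects that the documents do not give. The case for regression adjustment is firmer than the case for restratifying the tests of proportions, because it costs almost nothing if history proves irrelevant.

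**What to change.** 1. Reconcile protocol exclusion 1 with SAP Appendix 1 item 1e, so that it is clear whether prior-season vaccination can vary among women enrolled in 2020-21.
2. In SAP 7.1, show prior-season influenza vaccination (yes/no/unknown) by arm. Confirm that the history as recorded identifies the previous season.
3. In SAP 8.3 EO5, name site and prior-season vaccination as covariates in the day-29 RIV4 versus IIV4 log-titre regression. Do the same for the EO6 cord-blood regression where numbers allow.
4. Keep the site-stratified Mantel-Haenszel tests as the main analysis of seroconversion and seroprotection. Add one supportive analysis adjusted for prior vaccination, rather than nine site-by-history strata.

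The cost is SAP wording and a little more analysis, plus a negligible loss of precision if history is not prognostic. If the previous season cannot be identified from the recorded history, some re-abstraction would be needed.
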